9.2.1 Pre-Treatment Specimens

Biopsy specimens obtained pre-treatment will be sent for single cell RNA sequencing, immunoprofiling via flow cytometry, multiplexed immunofluorescence and immunohistochemistry (IHC), and if adequate specimens are collected cytokine analysis/microfluidic culture. Please refer to the separate laboratory manual for specific collection and handling instructions.

In the event sufficient archival tissue is not available, WES will be performed on the pre-treatment biopsy sample in addition to the above testing. In this case, the germline blood sample obtained from participants during screening (any time prior to cycle 1 day 1) for WES should be sent for analysis **at the same time as the pre-treatment tissue sample**. Please refer to the laboratory manual for more detail.

9.2.2 On-Treatment Specimens

Biopsy specimens obtained on-treatment will be sent for single cell RNA sequencing immunoprofiling via flow cytometry, , multiplexed immunofluorescence and IHC, and if adequate specimens are collected cytokine analysis/microfluidic culture. Please refer to the laboratory manual for specific collection and handling instructions.

9.2.3 Time of Progression Specimens

Biopsy specimens obtained at the time of disease progression will be sent for WES, single cell RNA sequencing, immunoprofiling via flow cytometry, and multiplexed immunofluorescence and IHC. Please refer to the laboratory manual for specific collection and handling instructions.

9.2.4 Prioritization of Analyses

In the event that insufficient tumor tissue is obtained (e.g. the collected tumor tissue is scant, or the participant did not tolerate the biopsy procedure and it was aborted prior to collection of all of the core samples), priority of analyses will be as follows:

1. Performance of single cell RNA sequencing
2. Performance of immune profiling via flow cytometry
3. Performance of WES (applicable only to pre-treatment and time of progression samples)
4. Performance of multiplexed immunofluorescence and IHC
5. Performance of cytokine analysis/microfluidic culture

Collection of insufficient tumor tissue for analysis will not be considered a protocol violation.

9.3 Plasma Cytokine Analysis

Blood for performance of cytokine analysis will be collected from participants at the following time points:

- Baseline, to be collected any time prior to administration of the study drugs
- On day 1 of each subsequent cycle prior to administration of the study drugs
- At the off treatment visit

9.4 Peripheral Blood Mononuclear Cell Collection

Peripheral blood mononuclear cells (PBMCs) will be collected to examine T-cell responses in blood. Collection will occur at the following time points:

- Baseline, to be collected any time prior to administration of the study drugs
- On Cycle 2 Day 1 any time prior to administration of the study drugs
- At the off treatment visit

A total of 60 mL of blood will be collected at each time point. Please refer to the separate laboratory manual for specific collection and handling instructions.

10. STUDY CALENDAR

Baseline evaluations are to be conducted within 14 days prior to the start of protocol therapy. The informed consent and baseline tumor imaging may be obtained up to 28 days prior to the start of protocol therapy. In the event that the participant's condition is deteriorating, laboratory evaluations should be repeated within 48 hours prior to initiation of the next cycle of therapy.

Assessments must be performed prior to administration of any study agent.

Table 16: Study Calendar									
	Pre-Study	Cycle 1 Day 1	Cycle 1 Day 15 ^A	Cycle 1 Day 29 ^A	Cycle 2+ Day 1 ^B	Cycle 2+ Day 15 ^A	Cycle 2+ Day 29 ^A	Off Treatment ^C	Long-term Follow Up ^D
Informed consent	X								
Demographics	X								
Medical history	X								
Physical exam	X	X	X	X	X	X	X	X	
Vital signs ^E	X	X	X	X	X	X	X	X	
Height	X								
Weight	X	X	X	X	X	X	X	X	
ECOG Performance Status	X	X			X			X	
CBC w/diff, plts	X	X	X	X	X	X	X	X	
Serum chemistry ^F	X	X	X	X	X	X	X	X	
TSH	X				X				
ACTH	X				X				
Amylase and Lipase	X				X				
Adverse event evaluation	X	X-----X						X	
Radiologic evaluation	X	CT or MRI imaging of any disease-involved site. Imaging evaluations to be obtained at baseline and then every 6 weeks × 6 cycles (-3 day/+7 day scheduling window). Brain MRI is required for all patients at baseline, and every 12 weeks on study for patients with CNS disease. At the completion of 6 cycles of therapy, at the treating investigator's discretion, imaging may be moved to every 12 weeks (-14 day/+7 day scheduling window). Participants who discontinue treatment prior to documented disease progression should continue to be followed for radiologic response every 12 weeks until documented disease progression or death.						X	X
Serum β-HCG ^G	X								
Nivolumab Infusion ^H		X	X	X	X	X	X		
Ipilimumab Infusion ^H		X			X				

Table 16: Study Calendar									
	Pre-Study	Cycle 1 Day 1	Cycle 1 Day 15 ^A	Cycle 1 Day 29 ^A	Cycle 2+ Day 1 ^B	Cycle 2+ Day 15 ^A	Cycle 2+ Day 29 ^A	Off Treatment ^C	Long-term Follow Up ^D
Fresh Tumor Tissue Biopsy ^I	X			X ^I				X	
Archival Tumor Tissue Collection	X								
Plasma Collection	X				X			X	
PBMC Collection ^J	X				X			X	
Telephone or Care Provider Contact									X

A. A \pm 3 day scheduling window exists for this visit to accommodate vacations, holidays, adverse weather, or other scheduling difficulties.
 
B. The start of a subsequent cycle may be delayed by 7 days (+7 day window) to accommodate vacations, holidays, adverse weather, or other scheduling difficulties. The start of a subsequent cycle may also be moved up by 3 days (-3 day window) for scheduling issues.
 
C. Off-treatment evaluation. Note: follow up visits or other contact is required in order to identify SAEs during the 90 days following the last dose of ipilimumab and 100 days following the last dose of nivolumab. Participants removed from therapy due to adverse events must be followed at minimum until resolution or stabilization of the adverse event. Please refer to Section 5.6 for more detail.
 
D. Long-term follow up evaluation via telephone or care provider contact is required for survival status only for 3 years following documentation of disease progression, or until death. Contact to be performed every 3 months following the last dose of study treatment (\pm 1 month window).
 
E. Vital signs to include heart rate, blood pressure, temperature, and respiratory rate.
 
F. Serum chemistry to include sodium, potassium, chloride, CO₂, blood urea nitrogen (BUN), creatinine, glucose, albumin, total protein, alkaline phosphatase, total bilirubin, SGOT [AST], and SGPT [ALT]. Other tests may be ordered as clinically indicated.
 
G. Serum pregnancy test only required for women of childbearing potential. Childbearing potential defined as any female who has experienced menarche and who has not undergone successful surgical sterilization (hysterectomy, bilateral tubal ligation, or bilateral oophorectomy) or is not postmenopausal (defined as amenorrhea >12 consecutive months; or women with a documented plasma follicle-stimulating hormone level $>35\mu\text{IU}/\text{mL}$).
 
H. Nivolumab and ipilimumab infusions to be administered as described in Section 5.
 
I. Fresh tumor tissue biopsy as described in Section 9. Biopsy required at baseline prior to the administration of any study agents, and again on Cycle 1 Day 29 (\pm 7 day scheduling window). An optional biopsy at the time of disease progression will also be offered to all participants. Note that a germline blood sample is required with the pre-treatment tumor biopsy as described in Section 9.
 
J. PBMC collection to occur at baseline (any time prior to the first study drug administration), on Cycle 2 Day 1, and at the off treatment visit as described in Section 9.
									

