2.2.6 Clinical Safety

Blockade of CTLA-4 by ipilimumab leads to T-cell activation, with the potential for clinical inflammatory adverse events (AEs) primarily involving the skin (dermatitis/pruritus), GI tract (diarrhea/colitis), liver (hepatitis), endocrine glands (e.g., hypophysitis and adrenal or thyroid abnormalities), and other less frequent organs (e.g., uveitis/episcleritis). The majority of these inflammatory AEs initially manifested during treatment; however, a minority occurred weeks to months after discontinuation of ipilimumab. The majority of the inflammatory AEs are reversible with the guidance issued in **Section 6**. In rare cases, these inflammatory AEs may be fatal.

Patients should be assessed for signs and symptoms of enterocolitis, dermatitis, neuropathy, and endocrinopathy, and clinical chemistries (including liver function, adrenocorticotrophic hormone [ACTH] level, and thyroid function tests) should be evaluated.

During evaluation of a suspected inflammatory AE, all efforts should be made to rule out neoplastic, infectious, metabolic, toxin, or other etiologic causes. Serological, immunological, imaging, and biopsy with histology (e.g., biopsy-proven lymphocytic) data should be used to support the diagnosis of an immune-mediated toxicity or support an alternative cause of the AE. In general, for severe inflammatory AEs, ipilimumab should be permanently discontinued, and systematic high-dose corticosteroid therapy should be initiated. For moderate immune-mediated AEs, ipilimumab should be held or delayed, and moderate-dose corticosteroids should be considered.

Based on limited current clinical experience, corticosteroids do not appear to adversely affect the anti-tumor response. For example, disease control was maintained in subjects with objective responses who received corticosteroid administration for concomitant serious inflammatory AEs.

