2.4.4 Clinical Safety

The original nivolumab plus ipilimumab combinations using the same dosing regimens as in the melanoma studies were found to be non-tolerable for the NSCLC population, so 4 additional regimens were examined (arms N, O, P, Q), and the results from these newer cohorts are presented. The regimens for these cohorts were:

- Arm N (n=31): nivolumab 1 mg/kg + ipilimumab 1 mg/kg every 3 weeks for 4 cycles, followed nivolumab 3 mg/kg every 2 weeks
- Arm O (n=40): nivolumab 1 mg/kg every 2 weeks + ipilimumab 1 mg/kg every 6 weeks
- Arm P (n= 38): nivolumab 3 mg/kg every 2 weeks + ipilimumab 1 mg/kg every 12 weeks
- Arm Q (n=39): nivolumab 3 mg/kg every 2 weeks + ipilimumab 1 mg/kg every 6

The most frequently reported drug-related adverse events (AEs) in the newer nivolumab plus ipilimumab cohorts were fatigue (29.0%), diarrhea (25.0%), pruritus (23.7%), and fatigue (23.1%) in arms N, O, P, Q, respectively. Drug-related serious adverse events (SAEs) reported in more than 2 subjects/cohort treated in the newer nivolumab plus ipilimumab cohorts were adrenal insufficiency, hypophysitis, pneumonitis, autoimmune hepatitis, diarrhea, colitis, and acute kidney injury.

Drug-related AEs leading to discontinuation reported in more than 1 subject treated in the new

nivolumab plus ipilimumab arms included ALT increased, AST increased, colitis, myalgia, pneumonitis, rash, autoimmune hepatitis, infusion-related reaction, facial nerve disorder, esophagitis, and transaminases increased.

Most deaths were due to disease progression. The only deaths reported due to study drug toxicity were in the nivolumab + ipilimumab original treatment groups (respiratory failure following Grade 3 colitis, pulmonary hemorrhage, and toxic epidermal necrolysis in a patient with history of ulcerative colitis).

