5. TREATMENT PLAN

5.1 Treatment Regimen

Nivolumab will be administered once every 2 weeks, on cycle days 1, 15, and 29. Ipilimumab will be administered once every 6 weeks, on cycle day 1. A treatment cycle is defined as 6 weeks or 42 days. Treatment will be administered on an outpatient basis. Reported adverse events and potential risks are described in **Section 7**. Appropriate dose modifications are described in **Section 6**.

Table 3: Regimen Description					
Agent	Premedications	Dose^A	Route^B	Schedule	Cycle Length
Ipilimumab	None	1 mg/kg	IV over 60 minutes (\pm 5 minute infusion window)	Day 1	42 days (6 weeks)
Nivolumab	None	3 mg/kg	IV over 60 minutes (\pm 5 minute infusion window)	Days 1, 15, 29	

A. Calculation of body surface area (BSA) should be performed per institutional standards of practice. Re-calculation of dosage for fluctuations in body weight should be made in accordance with institutional guidelines.
 
B. On days where both nivolumab and ipilimumab will be administered, nivolumab should be administered first. The ipilimumab infusion will start at least 30 minutes after completion of the nivolumab infusion.
					

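### TSH, ACTH, amylase and lipase are not scheduled at the Off Treatment visit, so a participant who stops before Cycle 2 Day 1 has no protocol-scheduled post-dose test

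*Combined protocol and SAP*

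**What the plan says.** In Table 16 the rows for TSH, ACTH and "Amylase and Lipase" are marked in two columns: Pre-Study and Cycle 2+ Day 1. They are blank at every Cycle 1 visit, at Days 15 and 29 of later cycles, at Off Treatment and in long-term follow-up. The rows for CBC, serum chemistry, ECOG status, plasma and PBMC are marked at Off Treatment. Note F's list of serum chemistry analytes contains none of the four tests, and no other note adds them.

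On timing, Section 10 states that "Assessments must be performed prior to administration of any study agent", and Section 5.1 that "A treatment cycle is defined as 6 weeks or 42 days". Note B gives the cycle start a window of +7 days, and "The start of a subsequent cycle may also be moved up by 3 days (-3 day window) for scheduling issues".

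On the reason to test, Section 2.2.6 says that "adrenocorticotrophic hormone [ACTH] level, and thyroid function tests) should be evaluated", without giving time points, and that of the inflammatory events "a minority occurred weeks to months after discontinuation of ipilimumab". Table 8 has its own entry for asymptomatic TSH change. Table 11 has separate rows for asymptomatic amylase or lipase elevation from Grade 1 to Grade 4. Section 7.1.1.1 lists thyroid disorders and raised lipase or amylase among the common events of the combination.

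After treatment, note C of Table 16 says "follow up visits or other contact is required in order to identify SAEs during the 90 days following the last dose of ipilimumab", and sets 100 days after the last nivolumab dose.

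**The concern.** Some of the events this protocol defines exist only if someone draws the blood. An asymptomatic TSH change or lipase rise cannot be reported by a participant or seen on examination. If the calendar does not schedule the assay after exposure, whether the event is recorded depends on whether the investigator had another reason to order it.

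The group most exposed to this is those who leave treatment during Cycle 1, some of them because of immune toxicity. Toxicity is a secondary objective (Section 13.1). Section 13.1.3 analyses it in everyone who received study drug, and Section 13.3.1 makes all participants evaluable from first dose. A participant with no post-dose assay therefore stays in the denominator with no scheduled chance to contribute an asymptomatic event to the numerator. Section 7.2.2 asks for non-serious events to be collected for at least 30 days after the last dose, yet no scheduled test in that period can show these.

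**Working it through.** There is no sample-size or power figure to reproduce. The check is a reading of the calendar and some date arithmetic.

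**1. Is the blank real?** The plasma row serves as a control. It is marked at Pre-Study and Cycle 2+ Day 1, like the three rows in question, and also at Off Treatment. The ECOG row is marked at Off Treatment too. The blanks are therefore not a shifted column.

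**2. First scheduled post-dose test.** Cycle 2 Day 1 = 42 + 1 = day 43. With the window it falls between day 43 − 3 = 40 and day 43 + 7 = 50.

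**3. Exposure before that test.** Nivolumab is given on days 1, 15 and 29 and ipilimumab on day 1 (Section 5.1): up to 3 and 1 infusions. Section 5.2.1 requires laboratory tests to be repeated on Cycle 1 Day 1 if screening values are more than 96 hours old, but that sample is also taken before dosing. Scheduled post-dose tests for someone who stops permanently before Cycle 2 Day 1: 0.

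**4. Later stoppers.** Take a participant who completes two cycles.
- Last nivolumab dose: Cycle 2 Day 29 = 43 + 28 = day 71.
- End of the nivolumab SAE window: 71 + 100 = day 171.
- If the Cycle 3 Day 1 sample is not taken, the last scheduled test is on day 43, and 171 − 43 = 128 days follow without one.
- If it is taken before the decision to stop, it falls on day 43 + 42 = 85, and the gap is 171 − 85 = 86 days.

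**5. How many participants?** The documents give no rate of stopping before Cycle 2 Day 1. Assuming 10 to 20% of 80, the number is 0.10 × 80 = 8 to 0.20 × 80 = 16.

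**6. Effect on a reported rate.** Let *p* be the true proportion with an asymptomatic abnormality and *f* the fraction with no post-dose test. If risk is the same in both groups and nobody in the untested group has a for-cause test, the all-treated analysis observes *p*(1 − *f*): 0.90*p* at *f* = 0.10 and 0.80*p* at *f* = 0.20. For-cause tests reduce the shortfall. A higher risk among early stoppers would increase it, and a lower risk after short exposure would reduce it.

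**The case against.** The strongest reply is that the protocol does not rely on the calendar alone. Table 8 calls for endocrine work-up when symptoms appear. Table 11 requires weekly amylase and lipase once an elevation is known and has a row for symptomatic cases. Note F allows other tests as clinically indicated, and participants removed for adverse events are followed to resolution or stabilization (Section 5.6). A reader might infer from Table 16 that early stoppers are never tested after dosing; these provisions show that this does not follow. Someone who stops in Cycle 1 with symptoms of endocrinopathy or pancreatitis is likely to be tested.

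Second, dose holds do not create the gap. Under Section 6.2 the assessment schedule runs on during a toxicity hold, so a participant on hold keeps the Cycle 2 Day 1 tests. Only permanent discontinuation matters.

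Third, Section 2.2.6 is background text without time points, so the calendar does not flatly contradict it. The SAEs listed in Section 2.4.4 ("adrenal insufficiency, hypophysitis, pneumonitis, autoimmune hepatitis, diarrhea, colitis, and acute kidney injury") are clinical events that note C's contact is meant to catch. They are not evidence that silent laboratory events are being missed.

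All of this stands, and it confines the point to scheduled testing and asymptomatic abnormalities. It does not remove the point. Symptom-triggered testing cannot systematically find the asymptomatic categories, Table 11's weekly monitoring begins only after an elevation has been found, note F is discretionary, and note C can be met by a contact without a blood draw.

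**Conclusion.** The gap is real, modest in size and cheap to close. A participant who permanently stops before day 43 has no protocol-scheduled post-dose TSH, ACTH, amylase or lipase, and a later stopper may have none after the last cycle's doses. Asymptomatic TSH and amylase/lipase abnormalities are therefore under-ascertained in the all-treated toxicity analysis. For ACTH the case rests on Section 2.2.6, since Table 8 defines no asymptomatic ACTH category.

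The 8 to 16 participants, and the 10 to 20% attenuation under equal risk and no for-cause testing, rest on an assumed early-stopping rate. The 128-day interval is one scenario, and 86 days is the other. Neither measures what an Off Treatment draw would recover, because the calendar does not date that visit. The primary endpoint is unaffected.

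A reader might also infer that laboratory event rates should use only tested participants as the denominator. The plan's all-treated population argues against that: where tests are ordered for cause, the tested group is enriched for symptomatic participants and the rate would be inflated.

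**What to change.** Reconcile Table 16 with Section 2.2.6 and Tables 8 and 11 by marking TSH, ACTH, amylase and lipase at the existing Off Treatment blood draw. In Section 13.1.3, keep all treated participants as the toxicity denominator, and state that for each assay the number with at least one post-dose result will be reported beside the rate.

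The cost is a calendar amendment and four assays, once per participant (at most 80 sets), on blood already being drawn. No visit or procedure is added, and no dose, hold or stopping rule changes. The downsides are a small laboratory cost, a few more low-grade abnormalities on record, and incomplete cover: a single draw does not span the 90 to 100 day SAE window and helps only those who attend the visit. The reporting change costs nothing and is useful even if the calendar stays as it is.

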2.3.1 Non-Clinical Summary

Nivolumab has been shown to bind specifically to the human PD-1 receptor and not to related members of the CD28 family. Nivolumab inhibits the interaction of PD-1 with its ligands, PD-L1 and PD-L2, resulting in enhanced T-cell proliferation and interferon-gamma (IFN- γ) release *in vitro*¹¹. Nivolumab binds with high affinity to activated human T-cells expressing cell surface PD-1 and to cynomolgus monkey PD-1. In a mixed lymphocyte reaction (MLR), nivolumab promoted a reproducible concentration-dependent enhancement of IFN- γ release¹².

In intravenous (IV) repeat-dose toxicology studies in cynomolgus monkeys, nivolumab was well tolerated at doses up to 50 mg/kg, administered weekly for 5 weeks, and at doses up to 50 mg/kg, administered twice weekly for 27 doses. While nivolumab alone was well tolerated in cynomolgus monkeys, combination studies have highlighted the potential for enhanced toxicity when combined with other immunostimulatory agents.

In addition, an enhanced pre- and postnatal development (ePPND) study in pregnant cynomolgus monkeys with nivolumab was conducted. Administration of nivolumab at up to 50 mg/kg 2QW was well tolerated by pregnant monkeys; however, nivolumab was determined to be a selective developmental toxicant when administered from the period of organogenesis to parturition at \geq 10 mg/kg (AUC_(0-168 h) 117,000 $\mu\text{g}\cdot\text{h}/\text{mL}$). Specifically, increased developmental mortality (including late gestational fetal losses and extreme prematurity with associated neonatal mortality) was noted in the absence of overt maternal toxicity. There were no nivolumab-related changes in surviving infants tested throughout the 6-month postnatal period. Although the cause of these pregnancy failures was undetermined, nivolumab-related effects on pregnancy maintenance are consistent with the established role of PD-L1 in maintaining fetomaternal tolerance in mice¹³.

Please refer to the nivolumab IB for further information on pre-clinical development.

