- 3.2.10 Participants with a condition requiring systemic treatment with corticosteroids of > 10 mg daily prednisone (or equivalent), or subjects requiring other immunosuppressive medications within 14 days of first treatment. Inhaled, topical, ophthalmologic, local steroid injections, and adrenal replacement steroid > 10 mg daily prednisone or equivalent are permitted in the absence of active autoimmune disease.
- 3.2.11 Participants with interstitial lung disease that is symptomatic or may interfere with the detection or management of suspected drug-related pulmonary toxicity in the opinion of the treating investigator.
- 3.2.12 Participants with a known history of testing positive for human immunodeficiency virus (HIV), or known acquired immunodeficiency syndrome (AIDS).
- 3.2.13 Participants with known positive test for hepatitis B or C indicating acute or chronic infection.
- 3.2.14 Participants with \geq Grade 2 peripheral neuropathy.

- 3.2.15 Uncontrolled intercurrent illness including, but not limited to, ongoing or active infection, symptomatic congestive heart failure, unstable angina pectoris, cardiac arrhythmia, or psychiatric illness/social situations that would limit compliance with study requirements.
- 3.2.16 Pregnant women are excluded from this study because ipilimumab and nivolumab are both agents with the potential for teratogenic or abortifacient effects. Because there is an unknown but potential risk for adverse events in nursing infants secondary to treatment of the mother with ipilimumab or nivolumab, breastfeeding should be discontinued if the mother is treated with ipilimumab or nivolumab. A negative serum pregnancy test is required prior to study entry.

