5.5 Criteria for Taking a Participant Off Protocol Therapy

Duration of therapy will depend on individual response, evidence of disease progression and

tolerance. In the absence of treatment delays due to adverse event(s), treatment may continue for a maximum of 24 months or until one of the following criteria applies:

- Disease progression, unless the participant meets the requirements outlined in **Section 5.5.1**.
- Intercurrent illness that prevents further administration of treatment
- The patient becomes pregnant or plans to become pregnant
- Unacceptable adverse event(s)
- Participant decides to withdraw from the protocol therapy
- General or specific changes in the participant's condition render the participant unacceptable for further treatment in the judgment of the treating investigator

Participants will be removed from the protocol therapy when any of these criteria apply. The reason for removal from protocol therapy, and the date the participant was removed, must be documented in the case report form (CRF). Alternative care options will be discussed with the participant.

When a participant is removed from protocol therapy and/or is off of the study, the relevant Off-Treatment/Off-Study information will be updated in OnCore.

In the event of unusual or life-threatening complications, treating investigators must immediately notify the Overall PI, [name] at [contact].

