7.2.5 Pregnancy

If, following initiation of the investigational product, it is subsequently discovered that a study participant is pregnant or may have been pregnant at the time of investigational product exposure, including during at least 5 half-lives after product administration, the investigational product will be permanently discontinued in an appropriate manner (e.g., dose tapering if necessary for participant).

The investigator must immediately notify [contact] of this event via the Pregnancy Surveillance Form in accordance with SAE reporting procedures.

Protocol-required procedures for study discontinuation and follow-up must be performed on the participant.

Follow-up information regarding the course of the pregnancy, including perinatal and neonatal outcome and, where applicable, offspring information must be reported on the Pregnancy Surveillance Form (provided upon request from BMS).

Any pregnancy that occurs in a female partner of a male study participant should be reported to BMS. Information on this pregnancy will be collected on the Pregnancy Surveillance Form. In order for the principal investigator or designee to collect any pregnancy surveillance information from the female partner, the female partner must sign an informed consent form for disclosure of this information.

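### After study entry no pregnancy test is scheduled for women of childbearing potential, although treatment may run 24 months and must stop permanently for pregnancy

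*Combined protocol and SAP*

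**What the plan says.** **Testing.** In Section 10, Table 16, the serum beta-HCG row has a single mark, under Pre-Study. Note G reads "Serum pregnancy test only required for women of childbearing potential" and then defines childbearing potential; it gives no repeat schedule. Section 3.2.16 independently places the test before entry: "A negative serum pregnancy test is required prior to study entry". No other section schedules a later test.

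**Duration and stopping.** Under 5.5, "treatment may continue for a maximum of 24 months". The off-therapy criteria in the same section include "The patient becomes pregnant or plans to become pregnant". If a pregnancy is discovered, 7.2.5 says that "the investigational product will be permanently discontinued in an appropriate manner", and 7.7 requires a report within 24 hours.

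**Reason for caution.** Section 3.2.16 excludes pregnant women because "ipilimumab and nivolumab are both agents with the potential for teratogenic or abortifacient effects". Section 2.3.1 reports that in monkeys "nivolumab was determined to be a selective developmental toxicant when administered from the period of organogenesis to parturition" at 10 mg/kg or more. The trial dose of nivolumab is 3 mg/kg every 2 weeks (5.1).

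**What remains after entry.** Section 3.1.9 requires contraception and prompt reporting of a known or suspected pregnancy. Table 16 has a physical examination and weight at each two-weekly treatment visit, and note F allows other tests when clinically indicated.

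**The concern.** The rules on pregnancy are clear about what to do, but all of them start from a known pregnancy. The only scheduled means of finding one is used before the first dose. A site that follows the calendar exactly for two years would do no further test unless the participant or the clinician became suspicious.

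What is at stake is participant and fetal safety. If a pregnancy goes unrecognised, dosing continues until someone notices. The protocol's own account of the agents makes continued dosing undesirable, and the monkey losses followed dosing continued from organogenesis to parturition, so the number of further doses matters.

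**Working it through.** The plan states no figure on this point, so there is none to reproduce. The check counts how many doses one unrecognised pregnancy could receive, with and without a test each cycle.

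**Inputs from the protocol**
- Cycle of 42 days; nivolumab on Days 1, 15 and 29 (every 14 days); ipilimumab on Day 1 (every 42 days): 5.1.
- Maximum treatment of 24 months, taken as 730 days: 5.5.
- Assessments come before any study agent is given: Section 10. A pregnancy recognised at a visit is therefore taken to stop that day's dose, both with and without scheduled testing.

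**Assumptions not in the protocol**
- Time unrecognised, d: 6, 12 or 20 weeks.
- Time from conception until the assay turns positive, L: up to 14 days, or 15 to 28 days.
- Nominal dosing dates, ignoring visit windows and held doses.

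**Without scheduled testing.** The most doses in d days, with the recognition-day dose withheld, are d/14 rounded up for nivolumab and d/42 rounded up for ipilimumab.

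| Unrecognised for | Nivolumab | Ipilimumab |
|---|---|---|
| 6 weeks (42 days) | 42/14 = 3 | 42/42 = 1 |
| 12 weeks (84 days) | 84/14 = 6 | 84/42 = 2 |
| 20 weeks (140 days) | 140/14 = 10 | 140/42 = 3.3, so 4 |

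**With a pre-dose test on Day 1 of each cycle.** The worst case is conception just under L days before a Day 1 test that is still negative, found at the next Day 1, 42 days later.
- L up to 14 days: the doses are nivolumab on Days 1, 15 and 29 (3) and ipilimumab on Day 1 (1). The previous cycle's Day 29 dose falls 14 days before the test, so it precedes conception.
- L of 15 to 28 days: that earlier Day 29 dose is now included, giving 4 nivolumab and 1 ipilimumab.

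**Comparison.** At 6 weeks the ceiling without testing (3 and 1) is no higher than the ceiling with it (3 and 1, or 4 and 1). At 12 weeks, testing saves up to 3 nivolumab doses (6 − 3), or 2 with the slower assay (6 − 4), and 1 ipilimumab dose (2 − 1). At 20 weeks it saves up to 7 or 6 nivolumab doses (10 − 3, 10 − 4) and 3 ipilimumab doses (4 − 1). The gain arises only when a pregnancy would otherwise go unrecognised for longer than about one cycle.

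**Number of added tests.** Day 1 visits from Cycle 2 onward: 182/42 rounded down = 4 over 6 months, 365/42 = 8 over 12 months, 730/42 = 17 over 24 months.

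**Number of women concerned.** Table 19 plans 41 women but does not say how many are of childbearing potential, so no expected number of pregnancies can be derived.

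**The case against.** The strongest reply is that the protocol already has a chain of controls: a negative test at entry, contraception from consent to 23 weeks after the last dose, a duty to report suspicion at once, two-weekly visits with examination, discretionary testing, and stopping even for a planned pregnancy. Nothing in the documents obliges the sponsor to test each cycle. Few or none of the 41 planned women may be of childbearing potential, and if pregnancies are recognised within about six weeks the added test saves no doses. All of this stands, and it is why the point is small. It does not close the gap: every control after entry depends on prevention or suspicion, and the expected toxicities in 7.1.1.1 include fatigue, nausea and vomiting, which early pregnancy can also cause.

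Several stronger readings are tempting and should not be drawn:
- **That the protocol contradicts itself.** It does not. The entry test, the stopping rule and the reporting rule are compatible; what is missing is a scheduled means of detection.
- **That examination would miss a pregnancy because the developmental mortality in monkeys "was noted in the absence of overt maternal toxicity".** That phrase means that the drug did not visibly harm the mother. It says nothing about whether an examination can detect pregnancy.
- **That dosing could continue to term.** This would require every two-weekly examination and weight to miss an entire pregnancy, and the documents give no reason to expect it.
- **That the monkey findings apply directly at the trial dose.** They arose at 10 mg/kg or more, above the 3 mg/kg used here.
- **That the first dose is unprotected.** Section 5.2.1 repeats laboratory tests more than 96 hours old and requires the values to meet eligibility again. It does not name beta-HCG, but it can be read to cover it.

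**Conclusion.** The point holds as an inexpensive safety improvement, not as an error in the plan. One test is scheduled, before treatment, and none during up to 24 months on therapy. Compared on the same basis, a Day 1 test each cycle lowers the ceiling from 6 nivolumab and 2 ipilimumab doses to 3 and 1 (or 4 and 1) for a pregnancy unrecognised for 12 weeks, and from 10 and 4 for one unrecognised for 20 weeks. It gives nothing at 6 weeks. These are ceilings for a single pregnancy and rest on assumed times unrecognised, assumed assay lags and the nominal schedule. Realistic exposure is likely to be near the low end, given the visit frequency and the reporting duty. The expected benefit across the trial cannot be estimated. The primary endpoint and all analyses are unaffected.

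**What to change.** In Table 16 and note G, for women of childbearing potential only, add serum beta-HCG on Day 1 of every cycle from Cycle 2. Use the blood draw already scheduled that day for TSH, ACTH, amylase and lipase, and require the result before either agent is given.

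The cost is one added mark in an existing table row, one sentence in a footnote, and at most 17 assays per such woman over 24 months (8 over 12 months, 4 over 6 months). Where the laboratory cannot report in time, the participant waits or has blood drawn shortly before the visit, which would then be an extra draw. An occasional false positive could delay a dose. If no woman of childbearing potential enrols, no assay is done.
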